### **6.3.1.2. TEAEs by System Organ Class and Preferred Term**

The following summary tables of TEAEs will be provided by SOC and PT using frequency counts and percentages (i.e., number and percentage of subjects with an event):

- All unsolicited TEAEs
- All unsolicited TEAEs that are treatment-related
- All serious TEAEs
- All serious TEAEs that are treatment-related
- All unsolicited TEAEs leading to discontinuation from study vaccine
- All unsolicited TEAEs leading to discontinuation from participation in the study
- All unsolicited Severe TEAEs
- All unsolicited Severe TEAEs that are treatment-related
- All unsolicited medically-attended TEAEs
- All unsolicited medically-attended TEAEs that are treatment-related
- All AESI of MIS-C
- All AESI of myocarditis and/or pericarditis
- All AESI other than MIS-C and myocarditis and/or pericarditis

### **6.3.1.3. TEAEs by System Organ Class, Preferred Term and Severity**

The following summary tables of TEAEs will be provided by SOC, PT, and maximum severity (mild < moderate < severe) using frequency counts and percentages:

- All unsolicited TEAEs
- All unsolicited TEAEs that are treatment-related
- Summary tables of TEAEs by SOC, PT, and severity (Any vs. Grade  $\geq 3$ ) will be provided as well.

### **6.3.2. Solicited Adverse Reactions**

An AR is any AE for which there is a reasonable possibility that the test product caused the AE. The term “Solicited Adverse Reactions” refers to selected signs and symptoms occurring after injection administration during a specified post-injection follow-up period

(day of injection and 6 subsequent days). The solicited ARs are recorded by the subject in eDiary. The occurrence and intensity of selected signs and symptoms is actively solicited from the participant during a specified post-injection follow-up period (day of injection and 6 subsequent days), using a pre-defined checklist (i.e., solicited ARs).

The following local ARs will be solicited by the eDiary: pain at injection site, erythema (redness) at injection site, swelling (hardness) at injection site, localized axillary swelling or tenderness ipsilateral to the injection arm, and groin or underarm swelling or tenderness ipsilateral to the side of injection.

The following systemic ARs will be solicited by the eDiary: headache, fatigue, myalgia (muscle aches all over the body), arthralgia (aching in several joints), nausea/vomiting, fever, chills, irritability/crying, sleepiness, and loss of appetite.

The AR categories are different for younger population between Age 37 months to <12 years and Age 6 months to  $\leq$  36 months. Details presented in Table 8 and 9 in the protocol.

The solicited ARs will be graded based on the grading scales presented in Table 8 and 9 in the protocol, modified from the Toxicity Grading Scale for Healthy Adult and Adolescent Volunteers Enrolled in Preventative Vaccine Clinical Trials (DHHS 2007). Investigator will assess Grade 4 events (with exception of fever).

If a solicited local or systemic AR continues beyond 7 days post injection, the participant's parent(s)/ LAR(s) will be prompted to capture details of the solicited local or systemic AR in the eDiary until it resolves or the next IP injection occurs, whichever occurs first.

All solicited ARs (local and systemic) will be considered causally related to injection.

After booster doses with mRNA-1273.214, local or systemic ARs will only be reported on the eCRF if they are medically attended, considered serious or lead to discontinuation from the study. No eDiaries will be used after booster doses with mRNA-1273.214.

Analyses of solicited ARs will be provided by age and treatment group for each injection (first or second) based on the associated subset of Solicited Safety Set, i.e. First (Second) Injection Solicited Safety Set; and for any injection based on the Solicited Safety Set, unless otherwise specified.

The number and percentage of subjects who reported each individual solicited local AR (has a toxicity grade of Grade 1 or greater) and solicited systemic AR (has a toxicity grade of Grade 1 or greater) during the 7-day follow-up period after each injection will be tabulated by age group, vaccination group, toxicity grade, and injection. The number and

percentage of subjects who reported each individual solicited AR will also be summarized by age group, vaccination group, toxicity grade, days of reporting and injection.

The number and percentage of subjects experiencing fever (a temperature greater than or equal to 38.0°C/100.4°F by the oral, axillary, or tympanic route) by toxicity grade will be provided.

A two-sided 95% exact confidence interval (CI) using the Clopper-Pearson method will be provided for the percentage of subjects who reported any solicited local AR, solicited systemic AR, or any solicited AR.

The onset of individual solicited AR is defined as the time point after each injection at which the respective solicited AR first occurred. The number and percentage of subjects with onset of individual solicited AR will be summarized by age group, vaccination group, study day relative to the corresponding injection (Day 1 through Day 7), and injection.

The duration will be calculated as the end date/day of the solicited AR event – start date/day of the solicited AR event + 1, regardless of whether it is intermittent or continued. If the solicited AR continues beyond 7 days, the days a solicited AR is reported after 7 days will be included (e.g., an event that lasted 5 days in the first 7 days post injection and 3 days beyond 7 days post injection, the duration will be reported as 8 (5+3) days.)

Solicited ARs collected on eDiary and those collected on reactogenicity aCRF will be provided in a listing, and the maximum grade from eDiary and aCRF will be presented. All solicited ARs that continue beyond 7 days post injection will be presented in separate data listings.

### **6.3.3. Pregnancy Tests**

A point-of-care urine pregnancy test will be performed, if deemed appropriate by the investigator, at the Screening Visit and before each vaccine dose in female participants of childbearing potential. At any time during the study, a pregnancy test either via blood or point-of-care urine can be performed, at the discretion of the investigator. A by-subject listing will be provided for pregnancy tests.

### **6.3.4. Physical Examinations**

A full physical examination, including body temperature (oral [for participants > 4 years of age] or tympanic [for participants ≤ 4 years of age]), length/height, weight and BMI will be presented in a listing.

## 6.4. Immunogenicity Analysis

The analyses of immunogenicity will be based on the PP Immunogenicity Subset for both parts and will be performed for each pediatric age group separately at the selected dose level in Part 1 and Part 2 based on the participants in the PP Immunogenicity Subset. The PP Immunogenicity Subset is the primary analysis population used in the immunogenicity analyses, unless otherwise specified. For each pediatric age group, participants from Part 1 and Part 2 in the PP Immunogenicity Subset who receive the same mRNA-1273 dose level selected for expansion may be combined for immunogenicity analyses. If the same dose level is selected for expansion for more than one age group, these age groups may be combined for immunogenicity analyses.

The GMT and geometric mean (GM) level will be calculated using the following formula:

$$10^{\left\{ \frac{\sum_{i=1}^n \log_{10}(t_i)}{n} \right\}}$$

where  $t_1, t_2, \dots, t_n$  are  $n$  observed immunogenicity values.

The geometric mean fold-rise (GMFR) measures the changes in immunogenicity values within subjects. The GMFR will be calculated using the following formula:

$$10^{\left\{ \frac{\sum_{i=1}^n \log_{10}\left(\frac{v_{ij}}{v_{ik}}\right)}{n} \right\}} = 10^{\left\{ \frac{\sum_{i=1}^n \log_{10}(v_{ij}) - \log_{10}(v_{ik})}{n} \right\}}$$

where, for  $n$  subjects,  $v_{ij}$  and  $v_{ik}$  are observed immunogenicity values for subject  $i$  at time points  $j$  and  $k$ ,  $j \neq k$ , where  $j$  represent pre-injection baseline at Day 1.

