#### **6.4.3. Secondary Analysis of Antibody-Mediated Immunogenicity Endpoints**

For each group, the following evaluations will be performed at each time point at which blood samples are collected for immunogenicity (unless otherwise specified).

- GM level of anti-SARS-CoV-2-specific bAb with corresponding 95% CI will be provided at each time point. The 95% CIs will be calculated based on the t-distribution of the log-transformed values then back transformed to the original scale for presentation. The following descriptive statistics will be also provided at each time point: the number of subjects (n), median, minimum and maximum.
- GM fold-rise (GMFR) of SARS-CoV-2-specific bAb levels with corresponding 95% CI will be provided at each post-baseline timepoint over pre-injection baseline at Day 1. The 95% CIs will be calculated based on the t-distribution of the log-transformed values then back transformed to the original scale for presentation. The following descriptive statistics will be also provided at each time point: the number of subjects (n), median, minimum and maximum.

Proportion of subjects with fold-rise  $\geq 2$ , and fold-rise  $\geq 4$  of serum SARS-CoV-2 specific bAb levels from Visit Day 1 (baseline) at each post injection time points will be tabulated with 2-sided 95% Clopper Pearson CIs

- GMT of SARS-CoV-2-specific nAb values with corresponding 95% CI will be provided at each time point using the same method mentioned above.
- GMFR of SARS-CoV-2-specific nAb values with corresponding 95% CI will be provided at each post-baseline timepoint over pre-injection baseline at Day 1 using the same method mentioned above.

Proportion of subjects with fold-rise  $\geq 2$ , and fold-rise  $\geq 4$  of serum nAb from Visit Day 1 (baseline) at each post-injection time points will be tabulated with 2-sided 95% Clopper-Pearson CIs.

- Proportion of subjects with seroresponse due to vaccination will be tabulated with 2-sided 95% Clopper-Pearson CIs at each post-baseline timepoint. The definition of seroresponse can be found in [Section 3.1](#).

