## **6.4. Immunogenicity Analysis**

The analyses of immunogenicity in long-term analysis at Day 1, Day 57, Day 209 and Day 394 (as applicable) will be based on the PP Immunogenicity Subset (Long-term Analysis) and Immunogenicity Subset (Long-term Analysis).

The analyses of immunogenicity in mRNA-1273 booster/third dose analysis will be based on

- PP Immunogenicity Subset with Pre-booster SARS-CoV-2 Negative for booster dose Analysis.

- PP Immunogenicity Subset (including Pre-booster/third dose SARS-CoV-2 Negative and Positive) for booster/third dose Analysis.

The PP Immunogenicity Subset with pre-booster SARS-CoV-2 negative will be used in the primary and secondary immunogenicity analyses for Part 1 and Part 2 booster dose analysis (Not applicable for Part 3 third dose analysis). And PP Immunogenicity Subset will be used for Part 3 third dose analysis, unless otherwise specified. The PP Immunogenicity Subset will be used in the immunogenicity analyses by pre-booster/third dose SARS-CoV-2 status (negative vs. positive).

The GMT and geometric mean (GM) level will be calculated using the following formula:

$$10^{\left\{ \frac{\sum_{i=1}^n \log_{10}(t_i)}{n} \right\}}$$

where  $t_1, t_2, \dots, t_n$  are  $n$  observed immunogenicity values or levels.

The geometric mean fold-rise (GMFR) measures the changes in immunogenicity values or levels within subjects. The GMFR will be calculated using the following formula:

$$10^{\left\{ \frac{\sum_{i=1}^n \log_{10}\left(\frac{v_{ij}}{v_{ik}}\right)}{n} \right\}} = 10^{\left\{ \frac{\sum_{i=1}^n \log_{10}(v_{ij}) - \log_{10}(v_{ik})}{n} \right\}}$$

where, for  $n$  subjects,  $v_{ij}$  and  $v_{ik}$  are observed immunogenicity values for subject  $i$  at time points  $j$  and  $k$ ,  $j \neq k$

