#### **6.4.4. Exploratory Analysis of Antibody-Mediated Immunogenicity Endpoints**

For each group applicable, the following evaluations will be performed at each time point at which blood samples are collected for immunogenicity antibody tests against SAS-CoV-2 prototype or variants of interest as applicable.

- GM level of SARS-CoV-2-specific Ab levels with corresponding 95% CI will be provided at each time point (e.g., Baseline [Pre-dose 1], Day 57, Day 209, Pre-booster/third dose, and BD-Day 29). The 95% CIs will be calculated based on the t-distribution of the log-transformed values then back transformed to the original scale for presentation. GM level will be plotted at each timepoint using boxplot. The following descriptive statistics will be also provided at each time point: the number of subjects (n), median, minimum and maximum.
- GM fold-rise of SARS-CoV-2-specific Ab levels with corresponding 95% CI will be provided at each timepoint over baseline (pre-dose 1) level, and post-booster/third dose timepoint over pre-dose 1 level and pre-booster/third dose level. The 95% CIs will be calculated based on the t-distribution of the log-transformed values then back transformed to the original scale for presentation. The following descriptive statistics will be also provided at each time point: the number of subjects (n), median, minimum and maximum.
- Proportion of subjects with seroresponse due to vaccination relative to pre-dose 1 will be tabulated with 2-sided 95% Clopper-Pearson CIs at each timepoint.

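### The GMFR formula in section 6.4 of the Part 1/Part 2 blinded-phase SAP labels the numerator index as baseline, so as printed it gives the reciprocal of the fold rise

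*SAP*

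**What the plan says.** There are two SAPs. The first covers the Part 1 open-label and Part 2 blinded phases; the second covers the Part 2 open-label phase, booster doses and Part 3.

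**First SAP, section 6.4.** The purpose is stated as follows: "The geometric mean fold-rise (GMFR) measures the changes in immunogenicity values within subjects". A computing rule comes next ("The GMFR will be calculated using the following formula"), printed in two equivalent forms: 10 to the mean of log10(v_ij/v_ik), and 10 to the mean of log10(v_ij) minus log10(v_ik). The closing clause then assigns the first index: j is to "represent pre-injection baseline at Day 1". The index k is not separately described.

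**First SAP, section 6.4.3.** For both binding and neutralizing antibody, GMFR with its 95% CI "will be provided at each post-baseline timepoint over pre-injection baseline at Day 1". The same section tabulates the proportions of subjects with a fold rise of at least 2 and at least 4 from Day 1.

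**Second SAP, section 6.4.** The same expression appears, with v_ij and v_ik described only as values at two different time points. Neither index is called baseline.

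**Second SAP, section 6.4.4.** The direction is given in words: fold rise "will be provided at each timepoint over baseline (pre-dose 1) level", and post-booster or post-third-dose values over both the pre-dose 1 and the pre-booster/third-dose level.

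**The concern.** In the first SAP the printed rule and the verbal description of the same output point in opposite directions. In the formula, v_ij is the numerator of the ratio and the first term of the log difference. Calling j the baseline therefore divides baseline by the post-injection value. Section 6.4.3 and the name fold rise both need the post-injection value divided by baseline.

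This is the only mathematical definition of GMFR in the first SAP, so it is what a programmer would code from and what an independent check would be compared with. Followed literally, a rise would be reported as a value below 1, and the confidence limits would become reciprocals in swapped order. A correctly programmed table would also fail a check against the formula as printed.

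**Working it through.** The plan states no expected GMFR, so there is no figure to reproduce. The check concerns the orientation of the formula.

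**Inputs**
- Numerator v_ij, denominator v_ik: first SAP, section 6.4, the same in both printed forms.
- j is the Day 1 pre-injection baseline: first SAP, section 6.4, closing clause. By elimination, k is the post-injection time point.
- Intended direction, post-injection over baseline: first SAP, section 6.4.3.

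**Algebra.** Write b_i for subject i's baseline value and p_i for the post-injection value.
- As printed (j = baseline): 10^{mean[log10(b_i) − log10(p_i)]} = 10^{−mean[log10(p_i/b_i)]} = 1/GMFR.
- As section 6.4.3 requires: 10^{mean[log10(p_i) − log10(b_i)]} = GMFR.

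The two results multiply to 1 for any data.

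**Numerical illustration** (invented titres, not from the documents)

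| Subject | Baseline | Post | Post/baseline | Baseline/post |
|---|---|---|---|---|
| 1 | 10 | 40 | 4 | 0.25 |
| 2 | 10 | 160 | 16 | 0.0625 |
| 3 | 20 | 320 | 16 | 0.0625 |
| 4 | 5 | 40 | 8 | 0.125 |

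- Intended: (4 × 16 × 16 × 8)^{1/4} = 8192^{1/4} = 9.514.
- As printed: (0.25 × 0.0625 × 0.0625 × 0.125)^{1/4} = 0.1051.
- Product: 1.000.

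The ratio form and the log-difference form give the same answer in each case, so the two sides of the printed equation agree with each other. The fault lies in the index label alone.

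**Confidence limits.** Section 6.4.3 computes the interval on the log scale and back-transforms it. Reversing the sign on the log scale turns an interval (L, U) into (1/U, 1/L). An invented interval of (40, 60) would become (1/60, 1/40) = (0.0167, 0.025). In the same way, a supposed 50-fold rise would print as 1/50 = 0.02.

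**Second SAP.** The expression is the same, but neither j nor k is assigned to baseline. A ratio of two unlabelled time points has no wrong direction, and section 6.4.4 supplies the direction in words.

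**The case against.** The strongest reply is that nobody would be misled. The quantity is called a fold rise, section 6.4.3 states the direction for binding antibody and again for neutralizing antibody, and the proportions with at least a 2-fold and 4-fold rise make sense only as post-injection over baseline. An inverted table would clash visibly with the geometric means and proportions beside it. This stands as a reason to rate the point low. It does not remove the contradiction, because the one formula given still says the opposite of the text.

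A second reply is that the point rests on a single subscript letter in a text read from PDF by a program. The orientation of the formula is corroborated by its two agreeing forms and by the identical expression in the second SAP. The labelling clause appears only once and cannot be checked against another copy. Nothing suggests that it was misread.

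Two stronger readings are tempting, and the documents do not support either:
- A reader might infer that neither SAP contains a correct GMFR formula. The second SAP's expression is generic rather than wrong. It has to serve two reference points (pre-dose 1 and pre-booster/third dose), so leaving the indices open is a reasonable choice.
- A reader might infer that every GMFR in the trial would be inverted. The wrong label sits only in the first SAP, and outputs under the second SAP are governed by its own unlabelled formula and its section 6.4.4.

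**Conclusion.** The point holds as an index-labelling error in section 6.4 of the first SAP. Followed as printed, the rule returns exactly the reciprocal of the GMFR and contradicts section 6.4.3. The reciprocal relation needs no assumption about the data; the titres, the 50-fold rise and the (40, 60) interval are illustrations only.

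The weight is small. GMFR is a descriptive summary. It is reported within the secondary analysis section, but section 3.2 does not list it as a secondary endpoint; section 3.3 lists it as exploratory. The co-primary GMR and seroresponse-rate comparisons in section 6.4.2 and the seroresponse definition in section 3.1 do not use this formula. No hypothesis test, noninferiority margin, alpha, power or sample size is affected. The documents do not show that any table was programmed in the wrong direction, only that the written rule would produce one if taken literally.

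**What to change.** In section 6.4 of the first SAP, change the closing clause so that k is the pre-injection Day 1 baseline and j is the post-injection time point. The formula itself can stay as printed, and it then agrees with section 6.4.3. On the illustrative data the corrected rule gives 9.514.

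Optionally, add to section 6.4 of the second SAP that k is the pre-Dose 1 or the pre-booster/third-dose time point, as applicable, so that the formula matches the two reference points in its section 6.4.4.

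The required change is one clause. It needs no new data, design change or re-powering. If GMFR programs or checks already exist, confirm that they divide the post-injection value by baseline.

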### 6.4.1. Immunogenicity Assessments

Immunogenicity assessments for both Part 1 and Part 2:

- Serum nAb value against SARS-CoV-2 as measured by pseudovirus and/or live virus neutralization assays.
- Serum bAb specific to the SARS-CoV-2 S protein.

- For Part 1, testing for serologic markers for SARS-CoV-2 infection using a nonvaccine antigen-based blood test at Day 1 (prior to the first dose), Day 57, Day 209, and Day 394.

Immunogenicity assessment for SARS-CoV-2 infection and CMI in Part 2:

- For Part 2, participants in each age group will be assigned to one of 5 phlebotomy cohorts (Table 2). Blood sampling will be performed in 3 of these 5 cohorts for immunogenicity at 3 of the following time points: Day 1 (prior to randomization and the first dose), Day 57, and one of Day 29 (prior to the second dose), Day 209, and Day 394. Participants in the fourth cohort (remainder of the age group) will provide a blood sample at Day 1 only (prior to randomization and the first dose). A fifth cohort of participants at selected VTEU sites only, will provide blood samples for assessment of exploratory serology and CMI on Day 1 (prior to randomization and the first dose), Day 43, Day 209, and Day 394.

#### **6.4.2. Primary Analysis of Antibody-Mediated Immunogenicity Endpoints**

If an accepted serum Antibody (Ab) threshold of protection against COVID-19 is available based on data from other mRNA-1273 studies or external data, the number and percentage of participants with Ab greater than or equal to the threshold at Day 57 will be provided with a 2-sided 95% CI using the Clopper-Pearson method. If the lower bound of the 95% CI on the mRNA-1273 group is > 70%, the primary immunogenicity objective of this study will be considered to be met for that age group.

The number and percentage of participants with serum Ab greater than or equal to the threshold with 2-sided 95% CI will be provided by age and vaccination group as defined in [Section 6.1](#) at each post baseline time point. The CI will be calculated using the Clopper-Pearson method.

If an accepted serum Ab threshold of protection against COVID-19 is not established, immune response as measured by GM value and seroresponse rate in each age group based on Day 57 Ab levels will be compared with that in young adults ( $\geq 18$  to 25 years of age) using data from Study P301. An analysis of covariance model will be carried out with Ab at Day 57 as dependent variable and a group variable (a pediatric age group in Study P204 versus young adults [ $\geq 18$  to 25 years of age] in Study P301) as the fixed variable for each pediatric age group. The GM values of the pediatric age group at Day 57 will be estimated by the geometric least square mean (GLSM) from the model. The GMR (ratio of GM values) will be estimated by the ratio of GLSM from the model. The corresponding 2-sided 95% CI

will be provided to assess the difference in immune response between the pediatric age group (Study P204) compared to the young adults ( $\geq 18$  to 25 years of age) in Study P301 at Day 57. For each pediatric age group, the noninferiority of GM value will be considered demonstrated if the lower bound of the 95% CI of the GMR is  $> 0.667$  based on the noninferiority margin of 1.5 and the GMR point estimate  $\geq 0.8$  (minimum threshold). In addition, GMR with 95% CI calculated using t-distribution will be provided to assess if the two methods are consistent in the analysis results.

The number and percentage of participants with seroresponse due to vaccination will be provided with 2-sided 95% CI using the Clopper-Pearson method at each post baseline time point with Day 57 being of the primary interest. The seroresponse rate difference with 95% CI using the Miettinen-Nurminen (score) confidence limits at Day 57 will be provided between children receiving mRNA-1273 in Study P204 and young adults of  $\geq 18$  to 25 years of age receiving mRNA-1273 from Study P301. For each pediatric age group, the noninferiority of seroresponse rate will be considered demonstrated if the lower bound of the 95% CI of the seroresponse rate difference is  $> -10\%$  based on the noninferiority margin of 10% and the seroresponse rate difference point estimate  $\geq -5\%$  (minimum threshold).

